#### 13.1.3. Informed Consent

For each study subject, written informed consent will be obtained before any protocol-related activities. As part of this procedure, the investigator or designee must explain orally and in writing the nature of the study; its purpose, procedures, and expected duration; alternative therapy available; and the benefits and risks involved in study participation. The subject should be informed that he/she may withdraw from the study at any time, and the subject will receive all information that is required by local regulations and ICH guidelines. The investigator will provide the sponsor or its representative with a copy of the IEC/IRB-approved ICF before the start of the study. The investigator shall retain the original, signed ICF in the subject's medical record and shall provide the subject with a copy of the consent.

If required by local or institutional policy, a biopsy consent form may also be utilized for the study kidney biopsy procedures. The biopsy-specific ICF should be from the center performing the biopsy, and it should be reviewed and signed at the same time as the study-specific ICF, covering the subject's consent to all 3 study biopsies. This biopsy-specific ICF is to specifically include the risks of the biopsy procedure, the planned anesthesia for the biopsy, the planned preprocedure evaluation, and the planned observation period following the biopsy. Within approximately 1 week of each biopsy procedure, the subject should be counseled again regarding the biopsy risks, planned anesthesia, required preprocedure laboratory values or tests, and observation period.

If there are any amendments to the approved protocol that may directly affect the subject's decision to continue participation in the study, the ICF will be amended accordingly, and the subject must re-sign the revised IEC/IRB-approved ICF.

## 13.2. Data Handling

The investigator must maintain all documentation related to this study. All essential documents (as defined in ICH Guideline E6) and the data generated in connection with this study, with the original copy of the final report, will be retained for at least 5 years after the last approval of a marketing application in an ICH region and until there are no pending or contemplated marketing applications in an ICH region or at least 5 years have elapsed since the formal discontinuation of clinical development of the investigational product. These documents should be retained for a longer period if required by the applicable regulatory requirements or by an agreement with the sponsor.

It is the responsibility of the sponsor to inform the investigator/institution as to when these documents no longer need to be retained.

#### 13.3. Source Documents

Source documents are considered to be all information in original records and certified copies of original records of clinical findings, observations, data, or other activities in a clinical study necessary for the reconstruction and evaluation of the study. The investigator will provide direct access to source documents and/or source data in the facilitation of trial-related monitoring, audits, review by IECs/IRBs, and regulatory inspections.

The investigator/institution should maintain adequate and accurate source documents and trial records that include all pertinent observations on each of the site's trial subjects. Source data should be attributable, legible, contemporaneous, original, accurate, and complete. Changes to source data should be traceable, not obscure the original entry, and be explained, if necessary.

#### 13.4. Record Retention

Study records and source documents must be preserved for at least 15 years after the completion or discontinuation of/withdrawal from the study, at least 2 years after the drug being studied has received its last approval for sale, or at least 2 years after the drug development has stopped, and in accordance with the applicable local privacy laws, whichever is the longer time period.

The investigator agrees to comply with all applicable federal, state, and local laws and regulations relating to the privacy of patient health information, including, but not limited to, the Standards for Privacy of Individually Identifiable Health Information; Title 45 of the US Code of Federal Regulations, Parts 160 and 164; and the Health Insurance Portability Accountability Act of 1996 Privacy Rule. The investigator shall ensure that study subjects authorize the use and disclosure of protected health information in accordance with the Health Insurance Portability Accountability Act of 1996 Privacy Rule and in a form satisfactory to the sponsor.

## 13.5. Monitoring

On-site monitoring will be performed by the sponsor's designee for the duration of the study. The monitor will ensure that the study is conducted, recorded, and reported, in accordance with the protocol, standard operating procedures (SOPs), GCP, and the applicable regulatory

requirements. The monitor will verify the accuracy and completeness of the eCRF entries, source documents, and other study-related records against each other. The investigator will provide direct access to source data/documents for study-related monitoring. It is important that the investigator and the staff are available at these visits. The monitor will record the date of each visit, with a summary of the status and progress of the study. Proposed actions will be documented in writing to the investigator.

### 13.6. Quality Control and Quality Assurance

The sponsor or its designee will perform the quality assurance and quality control activities of this study; however, responsibility for the accuracy, completeness, security, and reliability of the study data presented to the sponsor lies with the investigator generating the data.

Quality control and quality assurance systems are implemented and maintained using written SOPs from the investigative site, the sponsor, and/or its designee to ensure that the study is conducted and data are generated, documented (recorded), and reported in compliance with the protocol, GCP, and the applicable regulatory requirement(s), national and local laws, rules, and regulations.

Quality control checks will be applied at each stage of data handling (eg, edit checks) to ensure that all data are reliable and have been processed correctly.

The sponsor will arrange audits as part of the implementation of quality assurance to ensure that the study is being conducted in compliance with the protocol, SOPs, GCP, and all applicable regulatory requirements. Audits will be independent of and separate from the routine monitoring and quality control functions. Quality assurance procedures will be performed at study sites and during data management to assure that safety and efficacy data are adequate and well documented.

#### 13.7. Protocol Amendment and Protocol Deviation

#### 13.7.1. Protocol Amendment

Amendments to the protocol that entail corrections of typographical errors, clarifications of confusing wording, changes in study personnel, and minor modifications that have no effect on the safety of subjects or the conduct of the study will be classed as administrative amendments and will be submitted to the IEC/IRB for information only. The sponsor will ensure that acknowledgment is received and filed. Amendments that are classed as substantial amendments must be submitted to the appropriate regulatory authorities and the IECs/IRBs for approval and will not be implemented at sites until such approvals are received, other than in the case of an urgent safety measure.

#### 13.7.2. Protocol Deviations

Should a protocol deviation occur, the sponsor must be informed as soon as possible. Protocol deviations and/or violations and the reasons they occurred will be included in the clinical study report. Reporting of protocol deviations to the IRB/IEC and in accordance with applicable regulatory authority mandates is an investigator or contract research organization responsibility.

#### 13.8. Ethical Considerations

This study will be conducted in accordance with this protocol; the accepted version of the Declaration of Helsinki; all relevant federal regulations, as set forth in Parts 50, 56, 312, Subpart D, of Title 21 of the US Code of Federal Regulations and EU 536/2014, Annex 1, D, 17 (a); and in compliance with GCP guidelines.

Institutional ethics committees/IRBs will review and approve this protocol and the ICF.

All subjects are required to give written informed consent before participation in the study.

### 13.9. Confidentiality

Confidentiality of subject's information must be maintained, in accordance with national and local privacy laws.

## 13.10. ClinicalTrials.gov

This study has been listed with Clinical Trials.gov, as required.

## 13.11. Study Termination

The sponsor reserves the right to suspend or discontinue this study for administrative and/or safety reasons at any time. The investigator reserves the right to discontinue dosing subjects at any time for safety reasons.

## 13.12. Financing and Insurance

A clinical trial agreement between the investigator/institution and the sponsor will address all finance and insurance matters.

## 13.13. Publication Policy/Disclosure of Data

Both the use of data and the publication policy are detailed within the clinical study agreement. Intellectual property rights (and related matters) generated by the investigator and others performing the clinical study will be subject to the terms of a clinical study agreement that will be agreed between the institution and the sponsor or its designee. With respect to such rights, the sponsor or its designee will solely own all rights and interests in any materials, data, and intellectual property rights developed by investigators and others performing the clinical study described in this protocol, subject to the terms of any such agreement. In order to facilitate such ownership, investigators will be required to assign all such inventions either to their institution or directly to the sponsor or its designee, as will be set forth in the clinical study agreement.

# 15. APPENDICES

### APPENDIX 1. LONG-TERM EXTENSION ACTIVITIES

## 15.1. Part B: Long-Term Extension

This appendix contains only information that is specific to the design and conduct of Part B, the long-term extension. Any processes, procedure, or information not described in this appendix is identical to that described through the body of the main protocol.

### 15.1.1. Part B Overview/Rationale

Following Week 52 and the completion of Part A (the core study), any subject who, in the opinion of the investigator, is experiencing clinical benefit from pegcetacoplan administration will be invited to participate in Part B, the long-term extension, in order to continue to receive treatment with pegcetacoplan until it is commercially available for the disease under study. Dosing will remain the same throughout Part A and Part B.

Table 7 contains the Schedule of Activities for visits that will be conducted during Part B, the long-term extension.

Table 7: Schedule of Activities for Part B, Long-Term Extension (Following Week 52)

Study period	Long-term extension: Week 64 and beyond		ET & exit A
Study Week	64	≥76 B	
Study Day	448	532 B	
Study Visit	17B	18B B	
Visit window (±days)	7	7	
Physical examination C	X	X	X
12-lead ECG D	X		X
Infusion site/pump safety assessment E	X	X	
Concomitant medications	X	X	X
Vital sign measurements F	X	X	X
Urinalysis	X	X	X
Triplicate first-morning spot urine G (Dispense uPCR collection containers/arrange for home courier pickup)	х	х	X
Blood H			
PK sample	X	X	X
ADA assays I	X	X I	X
Hematology and chemistry	X	X	X
Complement profile	X	X	X
eGFR J	X	X	X
Pregnancy (β-HCG and FSH)			X
Urine pregnancy test K	X	X	X
Adverse events	X	X	X
Drug dispensation for home administration	X	X	

Abbreviations: β-HCG = β-human chorionic gonadotropin; ADA = antidrug antibody; CDK-EPI = Chronic Kidney Disease-Epidemiology Collaboration; ECG = electrocardiogram; eGFR = estimated glomerular filtration rate; ET = early termination; FSH = follicle-stimulating hormone; PK = pharmacokinetics; uPCR = urine protein-to-creatinine ratio.

- A. Subjects who discontinue treatment early should complete an ET visit immediately following discontinuation (but no later than 6 weeks after discontinuation of treatment) and an exit visit 6 weeks after the ET visit.
- B. Following Visit 18B (Week 76) subjects should continue to schedule visits at 12-week intervals (±7 days) indefinitely until the subject discontinues or the pegcetacoplan development program is terminated.
- C. Brief physical examinations should be performed at each visit, but symptom-driven physical examinations may also be performed at various unscheduled time points, if deemed necessary by the primary investigator. Edema should be assessed at every visit.
- ECGs are to be performed before dosing and before blood sampling procedures.
- E. Between site visits, subjects will be instructed to report any injection site reaction to the study coordinator.
- F. On clinic dosing days, vital signs will be measured within 2 hours prior to dosing, before venipuncture and ECG assessments.

- G. Starting at Visit 16 and continuing through the long-term extension, uPCR samples (first urinary output for the day) should be collected on 3 consecutive days, every 6 weeks, until the subject exits the study. At every clinic visit, the subject should be distributed 6 collection containers. For collections that happen between visits a courier service will be arranged for urine sample pickup and delivery to the site.
- H. Blood samples will be taken before dosing.
- Following Visit 18B (Week 76), ADA samples will be collected every 6 months (ie, at alternate visits).
   For subjects with positive anti-pegcetacoplan peptide antibody in last dose samples, additional samples will be collected 6 and 12 months after the last dose for further assessments.
- CKD-EPI creatinine equation (see https://www.niddk.nih.gov); the CKD-EPI creatinine-cystatin C equation (if confirmation required).
- K. Urine pregnancy test should be completed for women of childbearing potential prior to dosing.

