# 9.3. Follow-up Period

All subjects who complete study treatment and do not enter Part B, the long-term extension, will return to the investigator site for follow-up visits for 8 weeks, where assessments will be performed as per the Schedule of Activities (Table 1), and where the visit window allowances are also provided.

Subjects who discontinue treatment early and do not elect to continue their participation in the study will complete a follow-up visit 2 weeks after discontinuation of treatment and also the exit visit, 6 weeks thereafter.

The following assessments will be performed during this period, as outlined in the Schedule of Activities (Table 1):

- Procure 3 previously collected consecutive uPCR samples
  - Arrange courier pickup for all every 2-week triplicate uPCR samples during weeks without clinic visits
- Physical examination, brief
- Concomitant medications review
- Infusion site/pump safety assessment
- Blood samples for laboratory assessments
- Anti-pegcetacoplan peptide/anti-PEG circulating antibodies collection
- eGFR assessment
- Urinalysis collection

- Urine pregnancy test
- AE review
- Vital signs
- 12-lead ECG
- PK sample collection
- Dispense uPCR containers for consecutive collection every 2 weeks, per the following container dispersal schedule:
  - Dispense 3 containers (visits spaced every 2 weeks): Weeks 54, 56
  - Dispense 9 containers (visits spaced every 6 weeks): Weeks 58, 64, 70
- Dispense 24-hour urine collection container

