## 9.4. Exit Visit

All subjects will return to the clinic facility for the exit visit, 8 weeks following the final dose of pegcetacoplan, on Day 420 (or sooner if the subject discontinues prior to Week 52).

Study participation for each subject will be concluded following completion of the exit visit. If a subject withdraws from the study prior to the scheduled exit visit, all exit visit assessments should be performed at the subject's final visit to the clinic, including collection of blood samples for PK and/or PD assessments, as well as a postdose antigenicity sample, if not yet collected.

The exit visit procedures are listed in the Schedule of Activities (Table 1):

- Arrange courier service to pick up 24-hour urine collection to deliver to site
- Procure 3 previously collected consecutive uPCR samples to site
- Blood samples for laboratory assessments (see Schedule of Activities [Table 1] for details)
- Concomitant medications
- AE review
- Anti-pegcetacoplan/anti-PEG circulating antibodies assay
- eGFR assessment
- Urinalysis (see Schedule of Activities [Table 1] for details)
- Vital signs
- 12-lead ECG
- PK sample

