# 9.5. Early Termination and Exit Visit

Subjects who discontinue treatment early and do not elect to continue their participation in the study will complete an early termination visit. If the early termination visit is prior to Week 48, then all

assessments from Week 48, in addition to a renal biopsy, should be done, if possible. An additional exit visit should occur 6 weeks after the early termination visit. If the early termination is during the follow-up period, then all the assessments from the exit visit should be performed.

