# 11.2. Recording and Reporting Adverse Events

AEs and SAEs will be collected from the signing of the informed consent form (ICF) until the exit/early termination visit.

All SAEs will be followed until satisfactory resolution, until baseline level is reached, or until the SAE is considered by the investigator to be chronic or the subject is stable, as appropriate.

All SAEs that are suspected of being related to study treatment must be reported immediately to the sponsor if the investigator becomes aware of them, regardless of the time since the completion of the clinical trial.

Any events that occur prior to the start of dosing will be categorized as pretreatment events; events occurring after the start of dosing will be recorded as TEAEs (the start date of dosing and, therefore, categorization of the event will be dependent on randomization assignment).

For each AE, the investigator will evaluate and report the onset date (and time, if applicable), resolution date (and time, if applicable), intensity, causality, action taken, seriousness criteria met (if applicable), and whether or not the subject discontinued the study as a result of the event.

If possible, the outcome of any AE resulting in permanent discontinuation or that was present at the end of the study should be reported. Subjects experiencing AEs that cause interruption or discontinuation of investigational product and those experiencing AEs that are present at the last visit or early termination visit should receive follow-up as appropriate.

All SAEs must be reported to the sponsor/Apellis Safety by completing the SAE form within 24 hours of the investigator or their representative becoming aware of the event, whether or not the event is deemed treatment related. Completed SAE forms should be emailed to [contact].

AEs will be coded in accordance with the Medical Dictionary for Regulatory Activities (MedDRA). If known, the diagnosis of the underlying illness or disorder should be recorded, rather than its individual symptoms.

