# 12.4. Safety Analysis

TEAEs are defined as those AEs that develop or worsen after the first dose of study medication (or after randomization in Group 2) and up to 8 weeks beyond the last dose of study medication. All reported AEs will be coded using MedDRA and summarized by System Organ Class and Preferred Term. The number and incidence of TEAEs (both serious and nonserious) as well as the number and incidence of discontinuations due to TEAEs will be tabulated.

The AE summaries will be presented across all subjects. All AEs will be listed by subject, along with information regarding onset, duration, severity, relationship to study drug, action taken with study drug, treatment of event, and outcome. In addition, the number and incidence of rejection episodes and graft loss will be tabulated.

Changes from baseline in clinical laboratory tests will be summarized using descriptive statistics by visit and nominal time postdose. Out-of-range values will be flagged in data listings.

Changes from baseline in vital signs will be summarized using descriptive statistics by visit.

Changes from baseline in ECG parameters will be summarized using descriptive statistics by visit. Values of potential clinical significance will be flagged by listings.

Changes in physical examinations will be described in a data listing.

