### 15.1.2. Part B Study Design and Procedures

Following Visit 16 (Week 52), subjects who elect to continue in Part B, the long-term extension, will return to the site at 12-week intervals until pegcetacoplan is commercially available for the disease under study. Specific assessments for Part B are listed in Table 7.

The vaccination history for each subject should be reviewed prior to entry into the long-term extension, as described in Section 9.1.4, and any additional required vaccinations should be administered according to the current ACIP guidelines.

Subjects who discontinue treatment early should complete an early termination visit immediately following discontinuation (but no later than 6 weeks after discontinuation of treatment) and 1 exit visit 6 weeks after the early termination visit, as outlined in Table 7.

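### In Part B the exit visit has no minimum distance from the last dose, so adverse event collection can end some 10 to 11 days before the 56-day treatment-emergent window closes

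*Protocol*

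**What the plan says.** **Part B visits.** Footnote A to Table 7 (Protocol 15.1.1) asks a subject who stops treatment early for an early termination (ET) "visit immediately following discontinuation (but no later than 6 weeks after discontinuation of treatment) and an exit visit 6 weeks after the ET visit". Section 15.1.2 repeats the rule: "1 exit visit 6 weeks after the early termination visit". Neither place sets a minimum interval between the last dose and the exit visit.

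**What carries over from the main protocol.** Section 15.1 states: "Any processes, procedure, or information not described in this appendix is identical to that described through the body of the main protocol". The appendix gives its own timing for the exit visit, so that timing governs in Part B. It gives no rule of its own for when AE collection ends, so Section 11.2 applies: "AEs and SAEs will be collected from the signing of the informed consent form (ICF) until the exit/early termination visit". Table 7 marks adverse events in its ET and exit column.

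**Which events count.** Section 12.4 counts an event as treatment-emergent "up to 8 weeks beyond the last dose of study medication". SAP 7.1 gives the same limit as 56 days.

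**Part A, for comparison.** Under Section 9.3, subjects who stop early and leave the study "will complete a follow-up visit 2 weeks after discontinuation of treatment and also the exit visit, 6 weeks thereafter". Section 9.4 places the exit visit "8 weeks following the final dose of pegcetacoplan, on Day 420 (or sooner if the subject discontinues prior to Week 52"). Section 9.5 covers the same subjects as 9.3 but does not say when their ET visit takes place. It then adds: "An additional exit visit should occur 6 weeks after the early termination visit".

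**The concern.** Two clocks run from different starting points. The treatment-emergent window is counted from the last dose, and the end of AE collection in Part B is counted from the ET visit. If ET is prompt, as the footnote asks, the second clock stops first. The sites that follow the instruction most closely then give the shortest off-drug follow-up.

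No other scheduled visit fills the interval. Subjects in Part B are excused from the 8-week follow-up period (Section 6.2.3), and ET and exit are the only off-treatment visits in Table 7. New non-serious AEs, and serious AEs not suspected to be related, that start between an early exit visit and day 56 would meet the treatment-emergent definition, yet no contact is required at which they would be asked about.

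**Working it through.** **1. The plan's own figure.** The last main-period visit is Day 364. Adding 8 × 7 = 56 days gives Day 420, the exit day in Section 9.4. Section 9.3 gives 14 + 42 = 56 days. Both reproduce the 8-week standard.

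**2. Inputs for Part B.**
- Treatment-emergent window: 56 days from the last dose (Protocol 12.4, SAP 7.1).
- Exit visit: 6 × 7 = 42 days after ET (Table 7 footnote A, Section 15.1.2).
- L: days from last dose to ET. The footnote allows ET from at once to 42 days after discontinuation.

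**3. Formula.** Exit day = L + 42. Shortfall = max(0, 56 - (L + 42)) = max(0, 14 - L).

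| L (days) | Exit day | Shortfall (days) | Share of 56 days |
|---|---|---|---|
| 0 | 42 | 14 | 25.0% |
| 3 | 45 | 11 | 19.6% |
| 4 | 46 | 10 | 17.9% |
| 7 | 49 | 7 | 12.5% |
| 14 | 56 | 0 | 0% |
| 42 | 84 | 0 | 0% |

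**4. Which L is realistic.** Dosing is on Days 1 and 4 of each treatment week (Section 8.2), so doses are 3 or 4 days apart. A subject seen on the day the next dose would have been due has L = 3 or 4. L = 0 is improbable, because Table 7 asks for first-morning urine at ET and footnote G spreads that collection over 3 consecutive days. A long L also occurs: under Section 7.2.3, drug withheld for a liver abnormality is stopped permanently if the problem lasts more than 2 weeks, which makes L more than 14 and the gap zero.

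**5. Drug remaining.** The Amendment 3 rationale gives an effective half-life of 8 to 10 days. Assuming first-order decline, the fraction left at day 42 is 2^-(42/8) = 2.6% to 2^-(42/10) = 5.4%. At day 56 it is 2^-(56/8) = 0.8% to 2^-(56/10) = 2.1%.

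**6. After the change.** With exit at max(L + 42, 56), L = 0, 7, 14 and 42 give exit on days 56, 56, 56 and 84. The shortfall is zero in every case.

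**The case against.** The best reply is that 56 days is an outer limit for classifying events and does not promise that everyone is observed that long. Collection is governed separately by Section 11.2. This is right as far as it goes: a reader might infer that the documents contradict each other in Part B, and they do not. It still leaves days inside the window with no AE review required. The sponsor's own follow-up elsewhere is 8 weeks, adopted in Amendment 3 as sufficient for washout, and no reason is given for a shorter route in Part B.

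The second reply is that little would be lost, and most of this stands:
- Related serious AEs must be reported at any time, and AEs present at the last visit receive follow-up as appropriate (Section 11.2).
- An event that caused discontinuation is followed until it resolves or stabilizes (Section 7.2.2).
- Unscheduled visits are possible (Section 9.6).
- Antidrug antibody samples 6 and 12 weeks after the last treatment (Section 10.17), if carried into Part B, imply contact, though no AE review is stated there.
- By day 42 about 95% to 97% of the drug is gone. The amendment names no residual level that must be reached.
- The stated safety objective runs to 52 weeks. SAP 1 names Part B as a treatment phase, but SAP 3.5 times only the Week 12 and Week 52 analyses, and its AE columns are all Part A.

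These points limit the consequence. They do not close the gap for new non-serious AEs or unrelated serious AEs.

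**Conclusion.** The point holds for Part B and is minor, at the low end. Followed as written, Table 7 footnote A and Section 15.1.2 let AE collection end max(0, 14 - L) days before the treatment-emergent window closes. That is 10 or 11 days for ET on the day the next dose was due, and nothing from L = 14 onward. It could affect a few of at most 12 subjects, and no efficacy result changes. The result uses nominal visit days and takes the attended exit visit, not ET, as the end of collection.

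Three stronger readings are tempting, and the documents do not support them:
- **A typical loss of 14 days.** That figure requires ET on the day of the last dose.
- **The same gap in Part A.** Sections 9.3 and 9.4 both give 56 days. In 9.4 the allowance for an earlier date most naturally qualifies Day 420, not the 8 weeks. Section 9.5 would give an earlier exit only if its ET visit came before day 14, which it does not say. It agrees with the other two if ET is the 2-week visit of 9.3. This is an ambiguity of wording, not a demonstrated gap.
- **A shortfall in completers.** The ±7-day window at Visit 19 allows exit on Day 413, which is day 49 if the last dose was on Day 364. That dose date is an assumption: Day 4 of Week 52 is 51 × 7 + 4 = Day 361, which gives day 52. Either way this is ordinary visit tolerance.

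**What to change.** - **Table 7 footnote A and Section 15.1.2:** set the exit visit, or a final telephone AE contact, at the later of 6 weeks after ET and 56 days after the last dose, consent permitting.
- **Section 11.2:** state that AE collection runs through that final contact.
- **Section 9.5:** add a cross-reference saying that its ET visit is the 2-week visit of Section 9.3.

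The cost is protocol wording and, for each early discontinuer with L below 14, a slightly later visit or one telephone call. Nothing changes for subjects with L of 14 or more. The change cannot help subjects who withdraw consent, because Section 7.2.2 rules out further data collection from them.
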